1.3 CHANGES FROM PREVIOUS VERSIONS OF THE SAP

Protocol amendment v2.0 (dated 18 November 2021) states that an interim analysis will be conducted for part 1 and this SAP will reflect that change.

2 STUDY OBJECTIVES

Part 1 – Dose Escalation

Primary Objective:

- To evaluate the safety and tolerability of OMO-103 in adult patients with advanced solid tumours.

Secondary Objectives:

- To establish and confirm the recommended Phase 2 dose (RP2D) and dosing regimen of OMO-103 for further development.
- To characterise the pharmacokinetics (PK) of OMO-103.
- To evaluate preliminary anti-tumour activity in the dose escalation part.
- To assess the development of human anti-drug antibodies (ADA) to OMO-103.

Part 2 – Dose Expansion

Primary Objective:

- To assess the preliminary anti-tumour activity of OMO-103 monotherapy as measured by progression free survival (PFS) according to standard criteria (Response Evaluation Criteria in Solid Tumours [RECIST] v1.1 [Eisenhauer 2009]).

Secondary Objectives:

- To confirm the RP2D and dosing regimen of OMO-103 for further development.
- To assess the type, incidence, severity, timing, seriousness, and relatedness of adverse events (AEs) and laboratory abnormalities.
- To characterise the PK of OMO-103.
- To assess other efficacy parameters in patients with advanced solid tumours including disease control rate (DCR), objective response rate (ORR), overall survival (OS), time to progression (TTP), time to response (TTR) and duration of response (DOR) by RECIST v1.1.
- To assess the development of human ADA to OMO-103.
- To evaluate the effect of OMO-103 on Quality of Life (QoL) measured by the Quality of Life questionnaire.

Exploratory (Both Parts 1 and 2):

- Evaluation of potential biomarkers.
- Myc expression levels.

3 STUDY DESIGN

3.1 OVERVIEW

This study is an open label, two-part, FIH Phase 1/2a dose-finding study designed to determine the safety, tolerability, PK, PD and proof-of-concept of OMO-103 in patients with advanced solid tumours.

The study consists of two parts:

Part 1 - General

- Dose escalation in patients with solid tumours, including 5 or more OMO-103 dose levels. Approximately 11 to 24 patients in total will be enrolled in Part 1, covering 5 or more dose levels with the primary objective of determining the safety and tolerability of OMO-103 and defining an appropriate dose for further evaluation in Part 2.

The study will start with an accelerated-titration dose-escalation scheme enrolling one evaluable patient per cohort for the first 2 dose levels followed by a classic 3+3 design.

Part 1 - Timings and assessments

- Screening period: 28 days to 1 day prior 1st dose
- Treatment period:
 - Cycle 1 (Dose-limiting toxicity [DLT] period): CID1, CID2, CID3, CID4, CID5, (Days 3 to 5 only from dose level 3 onwards for PK evaluation), CID8, CID15, CID16/CID17 (Biopsy)
 - Cycle 2: C2D1, C2D8, C2D15
 - Cycle 3*: C3D1, C3D2, C3D3, C3D4, C3D5, (Days 3 to 5 only from dose level 3 onwards for PK evaluation), C3D8, C3D15
- *NOTE: Assumed 3 cycles but these are unlimited
- End-of-treatment (EOT) visit
- Follow-up period: 1-Month Follow-up visit

[figure not shown]
Part 2 - General

- Dose expansion where at least 3 parallel groups of patients with advanced Non-Small Cell Lung Cancer (NSCLC), Triple-Negative Breast Cancer (TNBC) and Colorectal Cancer (CRC) will be treated at the RP2D of OMO-103 to further characterise the safety, tolerability, PK, PD and anti-tumour activity of OMO-103.
Approximately 18 patients will be enrolled in each of the 3 parallel groups of patients (NSCLC, TNBC, CRC) in Part 2.

Part 2 - Timings and assessments

- Screening period: 28 days to 1 day prior 1st dose
- Treatment period:
 - Cycle 1: CID1, CID2, CID3, CID4, CID5, CID8, CID15
 - Cycle 2: C2D1, C2D8, C2D15, C2D16/C2D17 (Biopsy)
 - Cycle 3: C3D1, C3D2, C3D3, C3D4, C3D5, C3D8, C3D15,
 - Cycle 4: C4D1, C4D8, C4D15,
 - Cycle 5: C5D1, C5D8, C5D15,
 - Cycle 6*: C6D1, C6D2, C6D3, C6D4, C6D5, C6D8, C6D15,
- *NOTE: Assumed 6 cycles but these are unlimited
- EOT visit
- Follow-up period: 6-Month Follow-up period, including monthly visits if feasible. Telephone visits may be allowed if considered appropriate, e.g. hospice patients

Parts I/2 – Study Flowchart

* OMO-103, administered IV weekly (Q1W) and one cycle of treatment is 3 weeks (Q3W).

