- Male patients and their sexual partners must use an appropriate contraceptive from Screening for 4 months after last study drug administration.

**Total sample size:** In total, about 78 eligible patients will be enrolled.

**Number of planned visits:** Part 1: Dose Escalation

- **Screening period:** 28 days to 1 day prior 1st dose
- **Treatment period:**
  - Cycle 1 (DLT period): C1D1, C1D2, C1D3, C1D4, C1D5, (Days 3 to 5 only from dose level 3 onwards for PK evaluation), C1D8, C1D15, C1D16 or C1D17 (Day 16 or Day 17 for biopsy and only from dose level 3 onwards)
  - Cycle 2: C2D1, C2D8, C2D15

	
 
- Cycle 3*: C3D1, C3D2, C3D3, C3D4, C3D5, (Days 3 to 5 only from dose level 3 onwards for PK evaluation), C3D8, C3D15
 
 
*NOTE: Assumed 3 cycles but these are unlimited. The planned visits of other cycles will occur on D1, D8 and D15, except for every 3 cycles from Cycle 3 (i.e., Cycle 6, Cycle 9, etc. as PD biomarkers for target validation will be sampled on D1, as well as on D2 during these cycles).
 
 
- EOT visit
 
• Follow-up period: 1-Month Follow-up visit
 

	
Part 2: Dose Expansion
 
 
• Screening period: 28 days to 1 day prior 1st dose
 
• Treatment period: 
 
- Cycle 1: C1D1, C1D2, C1D8, C1D15
 
- Cycle 2: C2D1, C2D8, C2D15, C2D16 or C2D17 (Day 16 or Day 17 for biopsy)
 
- Cycle 3: C3D1, C3D2, C3D8, C3D15,
 
- Cycle 4: C4D1, C4D8, C4D15,
 
- Cycle 5: C5D1, C5D8, C5D15,
 
- Cycle 6*: C6D1, C6D2, C6D8, C6D15,
 
 
*NOTE: Assumed 6 cycles but these are unlimited. The planned visits of all other cycles will occur on D1, D8 and D15, except for every 3 cycles from Cycle 3 (i.e., Cycle 6, Cycle 9, etc. as PD biomarkers for target validation will be sampled on D1, as well as on D2 during these cycles).
 
 
- EOT visit
 
• Follow-up period: 6-Month Follow-up period, including monthly visits if feasible. Telephone visits may be allowed if considered appropriate, e.g., hospice patients
 
 
 

Safety parameters:	Physical examinations; vital signs assessments; ECOG performance status; laboratory analyses; autoimmunity; 12-Lead ECG; reported AEs.

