3.3.2 Study Flow Chart Part 2: Dose Expansion

Protocol Activities (Window, Days)	Screening	Treatment period							End of treatment ±3 days [1]	6-month follow-up (monthly visits ±3 days) [2]
		Cycle I				Cycle 2+ (unlimited)				
		28 days to 1 day prior 1 st dose	Day 1 ±1 day	Day 2	Day 8 ±1 day	Day 15 ±1 day [14]	Day 1 ±1 day	Day 8 ±1 day		
Baseline Documentation										
Informed Consent	X									
Eligibility Assessment	X									
Medical/Oncological History [3]	X									
Physical Examination [4]	X	X	X	X	X	X	X	X	X	X
ECOG Performance Status	X	X				X			X	X
12-Lead ECGs [7]	X	X				X			X	
Laboratory Studies										
Safety Blood Sampling [5]	X	X	X	X	X	X	X	X	X	X
Urinalysis [5]	X	X	X	X	X	X	X	X	X	X
PK Assessment [6]		X	X			X				
ADAs	X			X (Pre-dose)	X (Pre-dose)	X (Pre-dose)			X	X [16]

Study Flow Chart Part 2: Dose Expansion (continued)

Autoimmunity [12]	X					X			X	
Efficacy/PD Assessments										
CT/MRI [8]	X							C3 [8]	X	
Tumour Biopsy [9]	X							C2 D16 or D17 [9]	X (optional)	
PD markers [10]	X	X	X			X		C2 D16 or D17 [10]	X	X
PBMC blood PD markers [11]		X	X			X		C2 D16 or D17 [11]	X	X
Other Clinical Assessments										
Vital Signs	X	X	X	X	X	X	X	X	X	X
AEs/Con Meds and Treatments [13]	X	X	X	X	X	X	X	X	X	X
OMO-103 dosing [15]		X		X	X	X	X	X		

Footnotes for items [1]-[15] are listed in the protocol.

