11.3 EFFICACY ANALYSES

The primary efficacy endpoint of the study will be:

- Anti-tumour activity will be assessed by PFS using RECIST v1.1 assessed by the Investigator.

Secondary endpoints are:

- DOR
- DCR
- TTR
- TTP
- ORR

- OS (only Part 2).

All efficacy endpoints will be summarised and analysed descriptively, using the FAS and SAF populations. Kaplan Meier plots will be presented for time to event endpoints. Waterfall plots will be presented for RECIST data. The primary efficacy analysis will be repeated using the PP set.

Quality of Life Questionnaire:

Absolute values and change from baseline for total score will be presented using descriptive statistics for QoL Questionnaire scores. Overall there are 30 questions.

Only physical, emotional, fatigue and global related scores will be summarized.

Physical Functioning related questions are: Q1, Q2, Q3, Q4, Q5.

Emotional Functioning related questions are: Q21, Q22, Q23, Q24.

Fatigue relates questions are: Q10, Q12, Q18.

Global questions are: Q29, Q30.

Grouped scores for physical, emotional, fatigue, global scales and total scores will be normalised to the range 0-100 prior to being summarised.

All questions with the corresponding scores will be listed.

Other analysis:

- OMO-103 dosing will be summarised and listed using the SAF.

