		Complete Response	N	x
		Partial Response	N	x
	Overall (N=x)	DCR	Ratio (%)	x.x %
		Complete Response	N	x
		Partial Response	N	x
Stable Disease		N	x	
ORR.....				
TTP	Cohort 1 (Dose 0.48 mg/kg) (N=x)		N	X
			Mean	x.x
			SD	x.xxx
			Min	x

Parameter	Cohort	Component	Statistics	Result
			Median	x.x
			Max	X
TTR...	...			
DOR				

Source Listing: 16.2.7.2; Produced: yyyy-mm-ddThh:mm - Page x of y
Percentages are based on the total number of subjects within the Safety Set

*Programming note: A similar table will be presented for Table 14.2.2.2 (FAS) and Table 14.2.2.3 (PPS - Part 2 only)
Recommend one page be given to each of the 6 parameters (then repeated for 3 populations as above)
A similar table will be presented for Part 2 with Overall Survival (OS) included.*

OMO-103-01
Table 14.2.5
Dosing of OMO 103-101 - Part 1
Safety Set

Cohort	Statistic	
Cohort 1	n	x
	Mean	x.x
	SD	x.xx
	Min	x
	Median	x.x
	Max	x
Cohort 2	n	x
	Mean	x.x
	SD	x.xx
	Min	x
	Median	x.x
	Max	x
.....		

Source Listing: 16.2.5.1; Produced: yyyy-mm-ddThh:mm - Page x of y
Percentages are based on the total number of subjects within the Safety Set.

Programming note: A similar table will be presented (within the same table number) for Part 2 Dosing

OMO-103-01
Table 14.2.6
Change from Baseline: Quality of Life Questionnaire - Part 1
Safety Set

<Question's group> (Physical, Emotional, Fatigue, Global)

		COHORT 1 (Dose xx mg/ml) (N=x)	COHORT 2 (Dose xx mg/ml) (N=x)	...	Overall (N=xx)
Baseline	n	xx (xx.x %)	xx (xx.x %)		xx (xx.x %)
	Mean	xx.xx	xx.xx		xx.xx
	SD	xx.xx	xx.xx		xx.xx
	Minimum	xx.x	xx.x		xx.x
	Maximum	xx.x	xx.x		xx.x
	Median	xx.xx	xx.x		xx.xx
Visit	n	xx (xx.x %)	xx (xx.x %)		xx (xx.x %)
	Mean	xx.xx	xx.xx		xx.xx
	Etc				
Change from Baseline to Visit	n	xx (xx.x %)	xx (xx.x %)		xx (xx.x %)
	Mean	xx.xx	xx.xx		xx.xx
	Etc				
Etc					

Source Listing: 16.2.7.5; Produced: yyyy-mm-ddThh:mm - Page x of y
 The denominator for each percentage is the number of patients within the column.
 Physical functioning = sum of Q1, Q2, Q3, Q4 and Q5 scores.
 Emotional functioning = sum of Q21, Q22, Q23, and Q24 scores.
 Fatigue = sum of Q10, Q12 and Q18 scores.
 Global = sum of Q29 and Q30.

Programming note: A similar table will be presented for Part 2.

OMO-103-01
Figure 14.2.6.1
Kaplan-Meier Plot of Time from Start of IMP to TTP
Full Analysis Set

Figure Specifications

Procedure: PROC LIFETEST - survival plot

By: Treatment

x axis: Time

x axis: Label: Time Post-Dose (h)

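### Part 2 overall survival beyond month 6 is open to informative censoring, because follow-up appears to end 6 months after each patient's own end of treatment; the planned OS table does not handle censoring either

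*SAP*

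**What the plan says.** **Follow-up.** The Part 2 timings in SAP 3.1 end with the EOT visit and then "Follow-up period: 6-Month Follow-up period, including monthly visits if feasible". The protocol synopsis (Number of planned visits, Part 2) has the same: "6-Month Follow-up period, including monthly visits if feasible". In the Part 2 flow chart (SAP 3.3.2) the column "6-month follow-up (monthly visits" stands next to the end-of-treatment column. Its start is governed by footnote [2], which the SAP leaves to the protocol body; that text is not in the documents available here.

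**Treatment length.** SAP 3.1 says "NOTE: Assumed 6 cycles but these are unlimited", and "one cycle of treatment is 3 weeks".

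**OS.** OS is a Part 2 secondary endpoint (SAP 2 and 11.3). SAP 11.3 states that "Kaplan Meier plots will be presented for time to event endpoints". The figure list in SAP 14 has such plots only for TTP and TTR. For the table, the programming note in SAP 15 says "A similar table will be presented for Part 2 with Overall Survival (OS) included"; the shell it extends summarises time-to-event parameters by N, mean, SD, minimum, median and maximum. The SAP gives no OS start date and no OS censoring rule. Its only censoring statement is the footnote to the TTP figure, whose layout is reused for TTR.

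**The concern.** Kaplan-Meier is valid when leaving observation is unrelated to the risk of death. Here the planned end of observation would be time on treatment plus 6 months. A patient who stops after 3 cycles (3 × 3 = 9 weeks, about 2 months) is observed to about month 8. One who stops after 6 cycles (18 weeks, about 4 months) is observed to about month 10, and one treated for 12 months to month 18. In pretreated advanced cancer, early stopping usually means early progression and a worse outlook. After month 6 the risk set would therefore lose its poorer-prognosis survivors first, and the curve would flatten.

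At stake is any 12-month OS rate or median OS quoted from Part 2, and any informal comparison of NSCLC, TNBC and CRC if time on treatment differs between them.

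**Working it through.** **Inputs from the documents:** 6 months of follow-up after EOT; unlimited 3-week cycles; about 18 patients in each of 3 groups. The one design figure that can be reproduced is the total: 24 + 3 × 18 = 78, as stated. No OS rate, event count or precision target is given, so there is no OS figure to reproduce.

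**Assumptions (not in the documents):** time on treatment T and survival after EOT S are exponential, with medians m_T and m_S. OS = T + S, censored at T + 6 months. There are no deaths on treatment unless stated.

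**Step 1, earliest censoring.** T + 6 ≥ 6, so nobody reaches the planned end of follow-up before month 6. Up to then this mechanism causes no bias.

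**Step 2, one case in closed form (T and S independent).** Let a = ln2/m_T and b = ln2/m_S.

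- True OS: S(t) = [a·exp(−bt) − b·exp(−at)]/(a − b).
- After month 6 the risk set holds only patients on treatment or off it for less than 6 months. The off:on ratio is constant: r = a/(a − b) × [exp(6(a − b)) − 1].
- The Kaplan-Meier hazard is then h = b·r/(1 + r), and KM(t) = S(6)·exp(−h(t − 6)).

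With m_T = 2 and m_S = 6: a = 0.3466, b = 0.1155, r = 1.5 × (4 − 1) = 4.5, h = 0.1155 × 4.5/5.5 = 0.0945.

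- Month 6: S = (3 × 0.5 − 0.125)/2 = 0.6875.
- Month 12: true (3 × 0.25 − 0.0156)/2 = 0.367; KM 0.6875 × exp(−0.567) = 0.390. Excess 2.3 points.
- Month 18: true 0.187; KM 0.221. Excess 3.5 points.

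The cause is visible at month 12. Patients off treatment are (0.3672 − 0.0156)/0.3672 = 96% of all survivors, but 4.5/5.5 = 82% of the risk set.

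**Step 3, other settings (large simulations).** KM minus true OS:

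| Setting | 12 months | 18 months |
|---|---|---|
| Independent, m_T 2-4, m_S 4-8 | +2 to +4 points | +3 to +8 |
| Shared gamma frailty, variance 0.5, same grid | +4 to +6 | +8.5 to +13.5 |
| Medians 2 and 6, no frailty, on-treatment deaths, off/on hazard ratio 1 to 3 | 0 to +1 | about 0 to +1 |
| Death unrelated to treatment status | 0 (0.354 vs 0.353) | 0 |
| Correlation −0.3, m_T 2, m_S 4-10 | −1.4 to −4.5 | −2 to −10 |

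The difference at month 6 is zero in every row.

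**Step 4, median OS.** With frailty and medians that are 2 and 6 months in the whole group, true median OS is about 9.3 months against 10.4 by Kaplan-Meier. If 2 and 6 are set at average frailty instead, the result is 11.0 against 13.9, but the whole-group medians are then 2.4 and 7.2 months.

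**Step 5, the table shell.** With medians 2 and 6 and correlation 0.3, true median OS is 8.9 months. An uncensored summary gives 7.0 months from all recorded times, or 4.5 months from deaths only.

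**Step 6, precision with 18 patients (medians 2 and 6).** P(S > 6) = 0.5, so about 18 × 0.5 = 9 are censored. At month 12, 18 × 5.5 × 0.0156 = 1.5 remain at risk (up to 2.1 with correlation 0.6). The SD of the 12-month estimate is 0.14 to 0.17.

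**Step 7, check of the remedy.** With every patient followed to a common calendar cut-off (assumed 12 to 30 months after first dose), 12-month KM and true OS agree: 0.367 and 0.367, 0.365 and 0.365, 0.361 and 0.361 for correlation 0, 0.3 and 0.6.

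**The case against.** A reader might infer that survival follow-up definitely stops at EOT plus 6 months and that any Part 2 median OS would be too good. The documents do not support that much, for four reasons.

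- **The anchor is inferred.** It rests on the order of visits. Footnote [2] may define the start, or add later survival contact. This stands, and is why the point is conditional.
- **Direction depends on the analysis.** The upward bias belongs to a Kaplan-Meier estimate censored at last contact. The median that the OS table shell would produce is biased downward. No 9-, 12- or 18-month OS rate is planned in the text available.
- **Direction and size depend on prognosis.** If death is unrelated to treatment status there is no bias. With on-treatment deaths it shrinks to a point or less at 12 months, and with negative correlation it can reverse. Higher risk after early stopping is the plausible case, but no figure in the documents proves it.
- **Materiality.** OS is secondary and descriptive, with no comparison planned. An SD of 14 to 17 points exceeds a bias of 2 to 6 points, and differences between groups from this cause would not be detectable. This stands. A confidence interval does not reveal a systematic error, though, and with about two patients at risk at 12 months there is little to quote in any case.

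It is also fair to say that suppressing every later curve would be one choice among several.

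**Conclusion.** The concern holds in conditional form. If follow-up is counted from each patient's own EOT and OS is estimated by Kaplan-Meier censored at last contact, OS beyond month 6 is subject to informative censoring and is likely overestimated. The size rests wholly on the assumptions listed above: about 2 to 6 points at 12 months without on-treatment deaths, about 0 to 1 with them (medians 2 and 6, no frailty), and about 1 month on the median in the frailty example. The sign is not guaranteed.

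The gap in the SAP does not depend on those assumptions: OS has no start date and no censoring rule, and its table shell cannot handle censored times. Of the two planned displays, one probably overstates late OS and the other understates it. Only OS to month 6 is free of this mechanism, and even that assumes the scheduled contacts take place, since monthly visits are required only where feasible. This is a worthwhile, inexpensive correction to a descriptive secondary endpoint; it does not threaten the trial's main conclusions.

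**What to change.** **SAP wording only.** In 11.3 and the Part 2 versions of Tables 14.2.2.1 to 14.2.2.3:

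- Define OS as time from first dose to death from any cause, censored at the date last known alive.
- Replace mean, SD, minimum and maximum for OS with Kaplan-Meier estimates, and add the numbers of deaths and censored patients.
- Make the 6-month OS rate with 95% CI the OS summary.
- State when the 6-month follow-up starts, or cite the protocol text that does.
- Add the OS plot to the figure list, with numbers at risk. If any curve is shown beyond month 6 without common follow-up, add a statement that censoring depends on time on treatment.

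**Optional, by short amendment.** Collect survival status for all Part 2 patients at one common cut-off date and censor OS there. Only then quote a later OS rate or a median. Telephone visits are already permitted, so the cost is about one call or record check per patient not known to have died.

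**Downside.** Without the common cut-off check, no median OS is claimed from Part 2.

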3.2 INCLUSION AND EXCLUSION CRITERIA

To be eligible for inclusion into this study, each subject must fulfil all inclusion criteria and not violate any exclusion criteria (for the protocol version under which they are entered) during screening. Details of the inclusion and exclusion criteria are presented within the protocol (sections 10.2, 10.3).

3.3 STUDY TIMEPOINTS

3.3.1 Study Flow Chart Part I: Dose Escalation

Protocol Activities (Window, Days)	Screening 28 days to 1 day prior 1 st dose	Treatment period								End of treatment ±3 days [1]	1-month follow-up ±3 days [2]
		Cycle 1 (DLT period)					Cycle 2 + (unlimited)				
		Day 1 ±1 day	Day 2	Days 3, 4, 5 [16]	Day 8 ±1 day	Day 15 ±1 day [13]	Day 1 ±1 day	Day 8 ±1 day	Day 15 ±1 day [13]		
Baseline Documentation											
Informed Consent	X										
Eligibility Assessment	X										
Medical/Oncological History [3]	X										
Physical Examination [4]	X	X	X		X	X	X	X	X	X	X
ECOG Performance Status	X	X					X			X	X
12-Lead ECG [7]	X	X			X	X	X			X	
Laboratory Studies											
Safety Blood Sampling [5]	X	X	X		X	X	X	X	X	X	X
Urinalysis [5]	X	X	X		X	X	X	X	X	X	X
PK Assessment [6]		X	X (also for C3D2)	X (also for C3D3, C3D4, C3D5)			X				

Study Flow Chart Part I: Dose Escalation (continued)

ADAs	X				X (Pre-dose)	X (Pre-dose)	X (Pre-dose)			X	X
Autoimmunity [12]	X						X			X	
Efficacy/PD Assessments											
CT/MRI [8]	X								C3 [8]	X	
Tumour Biopsy [9]	X						D16 or D17 [9]			X (optional)	
PD markers [10]	X	X	X				X			X	
Other Clinical Assessments											
Hospital Admission [15]		X									
Vital Signs	X	X	X		X	X	X	X	X	X	X
AEs/Con Meds and Treatments [11]	X	X	X	X (AEs only)	X	X	X	X	X	X	X
OMO-103 dosing [14]		X			X	X	X	X	X		

Footnotes for items [1]-[15] are listed in the protocol.

3.3.2 Study Flow Chart Part 2: Dose Expansion

Protocol Activities (Window, Days)	Screening	Treatment period							End of treatment ±3 days [1]	6-month follow-up (monthly visits ±3 days) [2]
		Cycle I				Cycle 2+ (unlimited)				
		28 days to 1 day prior 1 st dose	Day 1 ±1 day	Day 2	Day 8 ±1 day	Day 15 ±1 day [14]	Day 1 ±1 day	Day 8 ±1 day		
Baseline Documentation										
Informed Consent	X									
Eligibility Assessment	X									
Medical/Oncological History [3]	X									
Physical Examination [4]	X	X	X	X	X	X	X	X	X	X
ECOG Performance Status	X	X				X			X	X
12-Lead ECGs [7]	X	X				X			X	
Laboratory Studies										
Safety Blood Sampling [5]	X	X	X	X	X	X	X	X	X	X
Urinalysis [5]	X	X	X	X	X	X	X	X	X	X
PK Assessment [6]		X	X			X				
ADAs	X			X (Pre-dose)	X (Pre-dose)	X (Pre-dose)			X	X [16]

Study Flow Chart Part 2: Dose Expansion (continued)

Autoimmunity [12]	X					X			X	
Efficacy/PD Assessments										
CT/MRI [8]	X							C3 [8]	X	
Tumour Biopsy [9]	X							C2 D16 or D17 [9]	X (optional)	
PD markers [10]	X	X	X			X		C2 D16 or D17 [10]	X	X
PBMC blood PD markers [11]		X	X			X		C2 D16 or D17 [11]	X	X
Other Clinical Assessments										
Vital Signs	X	X	X	X	X	X	X	X	X	X
AEs/Con Meds and Treatments [13]	X	X	X	X	X	X	X	X	X	X
OMO-103 dosing [15]		X		X	X	X	X	X		

Footnotes for items [1]-[15] are listed in the protocol.

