4 STUDY VARIABLES AND COVARIATES

4.1 PRIMARY VARIABLES

The primary endpoints are as follows:

Part 1: Dose Escalation:

- Number of patients with a DLT;
- Number of patients with ≥ 1 related AE;
- Number of patients discontinuing study treatment due to related AEs.

The RP2D will be determined at the conclusion of Part 1.

Part 2: Dose Expansion

- Progression free survival (PFS) based on RECIST v1.1 as assessed by the Investigator.

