Programming note: A similar table will be presented for Part 2 (Dose expansion)

OMO-103-01
Table 14.1.2.1
Summary of Demographic and Baseline Information - Part 1
Safety Set

Parameter	Statistic	All Subjects (N=x)
Age (yrs)	n	x
	Mean	x.x
	SD	x.xx
	Min	x
	Median	x.x
	Max	x
Height (cm)	n	x
	Mean	x.x
	SD	x.xx
	Min	x
	Median	x.x
	Max	x
Weight (kg)	n	x
	Mean	x.xx
	SD	x.xxx
	Min	x.x
	Median	x.xx
	Max	x.x
Number of pre-treatments per patient	n	x
	Mean	x.xx
	SD	x.xxx
	Min	x.x
	Median	x.xx
	Max	x.x

Source Listing: 16.2.4.1; Produced: yyyy-mm-ddThh:mm - Page x of y

Percentages are based on the total number of subjects within the Safety Set.

Programming note: A similar table will be presented for Part 2.

[Continued overleaf...]

OMO-103-01
Table 14.1.2.1
Summary of Demographic and Baseline Information - Part 1
Safety Set

Parameter		Statistic	All Subjects (N=x)
Race:	BLACK OR AFRICAN AMERICAN	n (%)	x (x.x)
	AMERICAN INDIAN OR ALASKA NATIVE	n (%)	x (x.x)
	ASIAN	n (%)	x (x.x)
	NATIVE HAWAIIAN OR OTHER PACIFIC ISLANDER	n (%)	x (x.x)
	WHITE	n (%)	x (x.x)
	MIXED	n (%)	x (x.x)
	OTHER	n (%)	x (x.x)
Gender:	M	n (%)	x (x.x)
	F	n (%)	x (x.x)

Source Listing: 16.2.4.1; Produced: yyyy-mm-ddThh:mm - Page x of y
Percentages are based on the total number of subjects within the Safety Set.

*Programming note: A similar table will be repeated for 14.1.2.2 (FAS).
A similar table will be presented for Part 2.*

OMO-103-01
Table 14.2.1.1
Summary of Progression Free Survival (PFS) - Part 1
Safety Set

Parameter	Cohort	Statistic	
PFS	Cohort 1 (Dose 0.48 mg/kg) (N=x)	n	x
		Mean	x.x
		SD	x.xx
		Min	x
		Median	x.x
		Max	x
	Cohort 2 (Dose 1.44 mg/kg) (N=x)	n	x
		Mean	x.x
		SD	x.xx
		Min	x
		Median	x.x
		Max	x
	Cohort ...		
	Overall (N=x)	n	x
		Mean	x.x
		SD	x.xx
		Min	x
		Median	x.x
Max		x	

Source Listing: 16.2.7.1; Produced: yyyy-mm-ddThh:mm - Page x of y
Percentages are based on the total number of subjects within the Safety Set.

*Programming note: A similar table will be presented for Table 14.2.1.2 (FAS) and Table 14.2.1.3 (PPS)
All tables will be repeated for Part 2.*

OMO-103-01
Table 14.2.2.1
Summary of Efficacy parameters, DCR, ORR, TTP, TTR and DOR - Part 1
Safety Set

Parameter	Cohort	Component	Statistics	Result
DCR	Cohort 1 (Dose 0.48 mg/kg) (N=x)	DCR	Ratio (%)	x.x %
		Complete Response	N	x
		Partial Response	N	x
	Cohort 2 (Dose 1.44 mg/kg) (N=x)	DCR	Ratio (%)	x.x %
		Complete Response	N	x
		Partial Response	N	x
	Cohort 2 Escalation ...	DCR	Ratio (%)	x.x %

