x axis: values: As appropriate

Y axis: Survival proportion

Y axis Label: Proportion without TTP

Y axis values: As appropriate

Legend:

(dose) OMO 103-101 (N=X) - linestyle = solid, colour = blue

The number of subjects at risk should be presented (option plots=survival(asterisk)).

Source Listing: 16.2.7.2; Produced: yyyy-mm-ddThh:mm - Page x of y
Censoring occurs where a subject did not record TTP within the study.

This layout also applies to:

Figures 14.2.6.2 (Repeat of above for PPS), 14.2.7.1 (Repeat of above for TTR), 14.2.7.2 (Repeat of 14.2.7.2 for PPS)

OMO-103-01
Table 14.3.1.1
Summary of Treatment Emergent Adverse Events - Part 1
Safety Set

	COHORT 1 (Dose xx mg/ml) (N=x)	COHORT 2 (Dose xx mg/ml) (N=x)	Overall (N=x)
Number (%) of subjects with TEAE by grade and relationship to study drug:				
GRADE 1	x (x.x)	x (x.x)	x (x.x)	x (x.x)
NOT RELATED	x (x.x)	x (x.x)	x (x.x)	x (x.x)
POSSIBLY RELATED	x (x.x)	x (x.x)	x (x.x)	x (x.x)
RELATED	x (x.x)	x (x.x)	x (x.x)	x (x.x)
GRADE 2	x (x.x)	x (x.x)	x (x.x)	x (x.x)
NOT RELATED	x (x.x)	x (x.x)	x (x.x)	x (x.x)
POSSIBLY RELATED	x (x.x)	x (x.x)	x (x.x)	x (x.x)
RELATED	x (x.x)	x (x.x)	x (x.x)	x (x.x)
GRADE ...	x (x.x)	x (x.x)	x (x.x)	x (x.x)

Source Listing: 16.2.8.1; Produced: yyyy-mm-ddThh:mm - Page x of y

A subject with multiple adverse events is counted only once at the maximum level of severity or the strongest relationship to study drug.

Percentages will be calculated from the number of subjects in the Safety Set within a cohort.

Programming note: A similar table will be presented for Part 2, with the column headers for each of the 3 groups. A similar table will be presented for Table 14.3.1.1a replacing patient counts by AE event counts.

OMO-103-01
Table 14.3.1.2
Summary of Treatment Emergent Adverse Events by System Organ Class and Preferred Term - Part 1
Safety Set

System Organ Class Preferred Term	Number of Events / Subjects (%)			
	COHORT 1 (Dose xx mg/ml) (N=x)	COHORT 2 (Dose xx mg/ml) (N=x)	Overall (N=x)
Any TEAEs	x / x (x.x)	x / x (x.x)	x / x (x.x)	x / x (x.x)
<SYSTEM ORGAN CLASS TERM> <PREFERRED TERM> <PREFERRED TERM>	x / x (x.x) x / x (x.x)	x / x (x.x) x / x (x.x)	x / x (x.x) x / x (x.x)	x / x (x.x) x / x (x.x)

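### The Part 2 flow chart schedules no CT/MRI after End of treatment although RECIST PFS is the primary endpoint, so patients who stop without progression may be censored informatively.

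*SAP*

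**What the plan says.** The SAP's Part 2 primary endpoint is "Progression free survival (PFS) based on RECIST v1.1 as assessed by the Investigator" (section 4.1). It replaces the protocol synopsis's ORR, as section 1.2 records.

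Section 3.1 gives Part 2 a "6-Month Follow-up period, including monthly visits if feasible", with telephone contact allowed. In the section 3.3.2 flow chart that column is headed "6-month follow-up (monthly visits ±3 days) [2". The CT/MRI row is marked at Screening, C3 and End of treatment, and is empty under follow-up. Physical examination, ECOG, safety bloods, urinalysis, ADAs, PD markers, PBMC markers, vital signs and AEs are all marked there. The CT/MRI row carries footnote [8] and the follow-up column footnote [2]. The SAP says of these: "Footnotes for items [1]-[15] are listed in the protocol".

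On analysis, section 11.3 states that "Kaplan Meier plots will be presented for time to event endpoints". The figures listed in section 14 cover only TTP and TTR. The shell "Summary of Progression Free Survival (PFS) - Part 1", to be repeated for Part 2, has n, mean, SD, minimum, median and maximum, with no Kaplan-Meier estimate and no count of censored patients. The only censoring statement is a note to the TTP figure, whose layout is reused for TTR: "Censoring occurs where a subject did not record TTP within the study". The SAP gives no event definition or censoring date for PFS, TTP or DOR, and no rule for new anticancer therapy.

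**The concern.** ORR needs few scans after treatment ends. PFS, TTP and DOR need them until progression. The disposition shell in section 15 allows for exits other than progression, among them adverse event, withdrawal by subject and physician decision. A patient who leaves that way, with no RECIST progression at the End of treatment scan, is followed for up to six months with no scheduled scan in the chart.

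If the reason for stopping is related to how soon the patient would progress, censoring at the last scan is informative. A death found in follow-up could supply a later PFS event, if PFS counts death, which the SAP does not say. It would not supply a progression date for TTP. The three endpoints are therefore not affected alike.

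With about 18 patients per group and no control arm, a few undated progressions can move the median that will be read as evidence of activity. Dates never collected cannot be recovered at analysis.

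**Working it through.** **1. The plan's own figures.** Part 2: 3 × 18 = 54. Total: 24 + 54 = 78. Both agree with SAP section 3.4. The documents give no expected PFS, event count, or rate of stopping without progression, so everything below rests on stated assumptions.

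**2. Patients affected.** Assume a share q of 10%, 20% or 30% stops without RECIST progression. Per group: 18 × 0.10 = 1.8, 18 × 0.20 = 3.6, 18 × 0.30 = 5.4, or about 2 to 5 patients. In all of Part 2: 5.4, 10.8 and 16.2 of 54.

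**3. Kaplan-Meier median when the hazard may change at stopping.** Assume exponential progression on treatment with median 3.0 months, so λ = ln 2 / 3 = 0.231 per month. Stopping has hazard μ = λq/(1 − q), so that a share q stops first. After stopping, the progression hazard is hλ. Assessment is continuous.

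- No scans after End of treatment: stoppers are censored at stopping. The Kaplan-Meier curve then estimates the on-treatment hazard, and its median is 3.0 whatever h is.
- Truth: S(t) = e^(−at) + μ(e^(−bt) − e^(−at))/(a − b), with a = λ + μ and b = hλ. The true median solves S(t) = 0.5.

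| h | True median at q = 10% / 20% / 30% | Error of the 3.0 estimate |
|---|---|---|
| 0.5 | 3.1 / 3.2 / 3.3 | −0.1 / −0.2 / −0.3 |
| 1 | 3.0 / 3.0 / 3.0 | none |
| 2 | 2.9 / 2.8 / 2.7 | +0.1 / +0.2 / +0.3 |
| 3 | 2.9 / 2.7 / 2.6 | +0.1 / +0.3 / +0.4 |

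Simulation with 200,000 patients per setting gives the same values. It also shows that six months of scans after stopping recovers the true median in each case. At assumed medians of 2 and 4 months the pattern is the same. The largest gaps are 2.0 against 1.7 and 4.0 against 3.4.

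**4. Kaplan-Meier median when every stopper is near progression.** Assume instead that each stopper is censored at a uniform point 50% to 100% of the way to that patient's own progression. For a true median of 3.0, the estimate is 3.3, 3.6 and 4.1 months at q = 10%, 20% and 30%, an error of up to 4.1 − 3.0 = 1.1 months.

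**5. Plain summaries, as in the PFS shell.** Take the recorded times as they stand.

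- Model of step 3: recorded times are exponential with rate λ + μ = λ/(1 − q). Their mean is (1 − q) × 3/ln 2 = 4.33(1 − q), which is 3.9, 3.5 and 3.0. Their median is 3(1 − q), which is 2.7, 2.4 and 2.1. The true mean is 4.33(1 − q) + 4.33q/h, larger by 4.33q/h in every case. At q = 20%, h = 2: 3.46 + 0.43 = 3.9 against 3.5. At q = 30%, h = 1: 3.03 + 1.30 = 4.3 against 3.0. The plain medians also lie below every true median in the table.
- Model of step 4: the mean is 4.33(1 − 0.25q), which is 4.2, 4.1 and 4.0 against 4.3. The plain median is about 2.9, 2.8 and 2.7 against 3.0.

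The plain summaries therefore fall even under the model that raises the Kaplan-Meier median most.

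**The case against.** The grid is not the whole scan schedule. It shows one on-treatment scan entry, C3, under a heading of unlimited cycles, so footnote [8] presumably carries timing rules that the grid does not. Footnote [2] governs the follow-up column. Both sit in protocol text not available here, and their absence from this text is not absence from the plan. This stands. A reader might infer from the empty cell that progression after stopping cannot be dated. The documents do not support that, because the footnotes may provide for scans.

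An End of treatment scan is planned, so a patient already progressing at that point is dated. This also stands, and it limits the problem to patients without RECIST progression at that scan.

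A reader might also infer that PFS, TTP and DOR are bound to come out too long. That requires stoppers to be closer to progression than those who continue. It is plausible for clinical deterioration and less certain for toxicity or withdrawal of consent. When stopping is unrelated to progression the Kaplan-Meier median is unbiased, and the statistics in the PFS shell move the other way.

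Finally, the study is exploratory, with a descriptive analysis and no PFS threshold, and the Part 2 interim rule in section 8 uses response. This limits the consequence. It does not remove the case for collecting dates that the primary endpoint needs. Even if the footnotes do require scans, the grid should show them, as it shows the other follow-up assessments.

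**Conclusion.** The point holds as a conditional one. As written, the Part 2 chart schedules no tumour assessment after End of treatment for a patient who has stopped without RECIST progression. The SAP's primary endpoint, and TTP and DOR with it, may therefore be censored informatively.

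The direction cannot be fixed in advance. On an assumed 3-month median and 10% to 30% stopping without progression, the Kaplan-Meier median is about 0.1 to 0.4 months too long if the hazard doubles or triples after stopping, and unbiased if the hazard is unchanged. It is about 0.1 to 0.3 months too short if the hazard halves. An error of about 1.1 months arises only at 30% and only if every stopper is already 50% to 100% of the way to progression. Plain means and medians are too short under all of these models.

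The median, the share stopping, the hazard after stopping and continuous assessment are all assumptions, and none is in the documents. The change is worth making because it is cheap and the dates cannot be recovered later.

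**What to change.** Check protocol footnotes [2] and [8] first. Unless they already provide it:

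- Mark tumour assessment in the follow-up column of the Part 2 flow chart for patients who stop without RECIST progression, until progression, new anticancer therapy, death or the end of the 6-month follow-up.
- Allow this to be met by recording scans done in routine care, with the Investigator's RECIST reading and the start date of any new anticancer therapy, at the monthly contacts already planned.
- Use these dates in PFS, TTP and DOR, with event and censoring dates defined for each.
- Report Kaplan-Meier estimates for these endpoints with the number censored by reason, in place of plain summaries alone.

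The cost is a change to the flow chart, CRF and table shells, plus some data entry and RECIST reading for a few patients, about 2 to 5 per group on the assumed rates. No visit, reader or procedure is added. The drawback is that routine scans fall at uneven times, so progression dates after stopping will be less regular than those on treatment.
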